Although the decreasing prevalence of Helicobacter Pylori (H. Pylori) worldwide, it remains high in the developing countries [1]. According to the most recent studies, the overall prevalence of H. Pylori in the developing countries is 50.8%, with the highest one presented in Africa (79.1%) [2, 3].

Unfortunately, the data on the prevalence of H. Pylori, are not available from all the countries of Africa. There is a paucity of information about the magnitude of the problem in Egypt, according to the few available studies, the prevalence is ranging from 71.7-91.7% [4, 5].

The importance of H. Pylori infection lies in the major role in chronic gastritis, gastric ulcer, and duodenal ulcer, up to gastric adenocarcinoma, and gastric mucosa-associated lymphoid tissue lymphoma [6].

Diagnosis of H. Pylori can be through invasive tests, which are cumbersome and expensive despite their high sensitivity and specificity. On the contrary, there are more easily and cheaper non-invasive tests, especially H. Pylori stool antigen and urea breath test have a higher sensitivity than serology [7].

The decreasing eradication rate of the standard triple therapy (STT) below 80% due to the emergence of resistant strains to Clarithromycin, raise the need for newer therapies that provide higher efficacy, and in the same time, better safety and compliance [8].

Bismuth-containing quadruple therapy came as the treatment of choice that avoids Clarithromycin use [9], but it was a non-reasonable option for the countries that are lacking in bismuth salts and/or tetracycline [10], beside of the

complex administration and low safety [11]. It raises the era of the competing sequential and concomitant non-bismuth (clarithromycin containing) quadruple treatments [12].

A novel two-step (dual-quadruple) treatment called the hybrid therapy (HT), which is actually a combined sequential and concomitant therapy, with a lower cost and better efficacy [13].

However, the adding of two drugs in the last seven days of the therapy may confuse the patient, making him less willing to complete the treatment that promote the idea of reversing the sequence (quadruple-dual) in what is called the reverse hybrid therapy (RHT), to simplify the treatment in one-step two-phase treatment [14].

Another non-Clarithromycin non-Bismuth quadruple therapy that is less complex and safer than bismuth quadruple therapy, which is called Levofloxacin quadruple therapy that contains levofloxacin, omeprazole, nitazoxanide, and doxycycline (LOND), showed promising results on the level of the cure rate and low drug resistance profile [15, 16].

Rational

As Helicobacter pylori is a common infection and a leading cause of gastric and duodenal ulcers with an increased incidence of gastric cancer, so we need an effective regimen as a first line in treatment of Helicobacter pylori.

Research questions

Which of the Hybrid, Reverse hybrid, and Levofloxacin quadruple therapies are more effective as a first-line eradication regimen for Helicobacter pylori in Egypt?

Hypothesis

The expected result of this study that Hybrid therapy is more effective than Reverse Hybrid and Levofloxacin quadruple therapies as a first-line eradication regimen for Helicobacter pylori infection in Egypt.

Aim of Work

We are aiming here to compare the Hybrid, Reverse hybrid, and Levofloxacin quadruple therapies as first-line therapy, trying to reach the safest, cost-effective, and compliance-inducing regimen in Egypt.

Objectives

- To assess the efficacy of Hybrid, reverse hybrid, and Levofloxacin quadruple therapies as a first line eradication regimen for Helicobacter pylori infection in Egypt.
- To evaluate the safety of each regimen.
- To determine which regimen has the best patient's compliance.

Subjects and Methods

Technical Design

A) The site of study:

The study will be conducted in Internal medicine department in Zagazig University Hospitals.

B) Sample size:

Assuming that the eradication rate in patients receiving Hybrid therapy is 91% versus 78.3% in Reverse Hybrid therapy. So, the sample size is 309 (103 in each group), using OPEN EPI at power 80% and C.I 95%.

C) Inclusion criteria:

- 1- Age more than 18 years.
- **2-** Both gender.
- **3-** Patient's approval to participate in the study.
- **4-** Patients with positive Helicobacter pylori antigen in the stool with no previous treatment for Helicobacter pylori.

D) Exclusion criteria

- **1-** Age < 18 years.
- **2-** Patients who refuse to participate in the study.
- **3-** Patients with previous treatment for Helicobacter pylori.
- **4-** Patients with known hypersensitivity to drugs used in regimens.

Tools of data collection

The following procedures were done to all enrollees:

1- Medical history to all patients.

- 2- Complete clinical examination.
- **3-** The fecal antigen test (FAT) which identifies H. pylori antigen in the stool by enzyme immunoassay was positive in all participants.

Operational design

- This is a randomized controlled (interventional) study conducted at Zagazig University Hospital, internal medicine department clinic after informed consent. All the patients are positive for H. pylori fecal antigen test.
- Steps of performance: (309) patients will be chosen from the Internal
 Medicine Department clinic, grouped into 3 groups:
 - Group 1: (103) patients will receive reverse hybrid regimen in the form of clarithromycin 500mg bid, omeprazole 20 mg bid, amoxicillin 1gm bid, and metronidazole 500 mg tid for 1 week, followed by omeprazole 20 mg bid, and amoxicillin 1gm bid in the 2nd week.
 - O Group2: (103) patients will receive hybrid regimen in the form of omeprazole 20 mg bid, and amoxicillin 1gm bid in the 1st week, then clarithromycin 500mg bid, omeprazole 20 mg bid, amoxicillin 1gm bid, and metronidazole 500 mg tid in the 2nd week.
 - Group3: (103) patients will receive Levofloxacin quadruple regimen
 (LOAD) in the form of nitazoxanide 500 mg bid, levofloxacin 250 mg QD, omeprazole 40 mg QD, and doxycycline 100 mg QD for 10 days

 Retesting by the fecal antigen test (FAT) after stopping the regimen by at least one month and withholding proton pump inhibitors for 2 weeks.

Administrative design

- Approval of medical department.
- Approval of the ethical committee in the faculty of medicine.
- Institutional Review Board (IRB) approval.
- Consent from the patient sheet.

Statistical analysis plan

The software SPSS (SPSS Inc., Chicago, Illinois, USA) version 19 for Windows will be used. Quantitative variables will be described using their means and standard deviations (Mean \pm SD). Categorical variables will be described using their absolute frequencies.

Comparison of categorical data will be performed using the Chi-square test and Fisher exact test when appropriate. Kolmogorov-Smirnov's (distribution-type) and Levene's (homogeneity of variances) tests will be used to verify assumptions for use in parametric tests. All normally distributed data will be interpreted using One-Way ANOVA F test. A nonparametric test (Kruskal-Wallis H Test) will be used to compare means when data is not normally distributed. A two-sided $(\alpha=2)$ p<0.05 will be considered significant. Additional tests according to the results will be used when appropriate.

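### The 80% power stated for 309 patients is about 72–73% for the only pair that was sized, and no levofloxacin rate is assumed although the hypothesis is that hybrid beats both other regimens

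*Combined protocol and SAP*

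**What the plan says.** The Hypothesis section expects that "Hybrid therapy is more effective than Reverse Hybrid and Levofloxacin quadruple therapies as a first-line eradication regimen". It therefore names two comparators for hybrid therapy.

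Technical Design, B) Sample size uses only one of them: "Assuming that the eradication rate in patients receiving Hybrid therapy is 91% versus 78.3% in Reverse Hybrid therapy". It then concludes: "So, the sample size is 309 (103 in each group), using OPEN EPI at power 80% and C.I 95". The levofloxacin group receives the same number without a calculation of its own. The only statement about how well that regimen works is in the introduction, where it is said to have "showed promising results on the level of the cure rate and low drug resistance profile". No rate is given.

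The Statistical analysis plan specifies a two-sided test with "p<0.05 will be considered significant". (The bracketed alpha prints as 2, but the 0.05 threshold and the two-sidedness are clear.) For proportions it says: "Comparison of categorical data will be performed using the Chi-square test and Fisher exact test when appropriate". It names no primary contrast, no pairwise plan and no adjustment for more than one comparison. No allowance for drop-out is stated.

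**The concern.** There are two separate problems.

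1. The stated power does not follow from the stated rates. A reader who takes the 80% at face value believes the hybrid versus reverse hybrid comparison is better protected against a false negative than it is.
2. Half of the hypothesis has no power statement. Whether 103 per group can separate hybrid from levofloxacin depends on a rate the protocol never assumes. Nothing in the analysis plan limits the 80% to one pair.

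The trial could therefore fail to support its own hypothesis through lack of power alone, and the protocol would not reveal this. A non-significant hybrid versus levofloxacin result would be hard to interpret without either the power or a confidence interval.

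**Working it through.** **Inputs from the documents.** Hybrid p1 = 0.91 and reverse hybrid p2 = 0.783, so d = 0.127. There are 103 per group, the target power is 80%, and the test is two-sided at 0.05. The levofloxacin rate is not given, so every value used for it below is an assumption. No drop-out is included.

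**Step 1: try to reproduce 103 per group.** For two proportions with pooled variance under the null:

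n = [1.960·√(2·p̄(1−p̄)) + 0.8416·√(p1(1−p1) + p2(1−p2))]² / d²

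- p̄ = (0.91 + 0.783)/2 = 0.8465, so 2·p̄(1−p̄) = 0.2599
- p1(1−p1) + p2(1−p2) = 0.0819 + 0.1699 = 0.2518
- n = (0.9992 + 0.4223)² / 0.01613 = 2.0206 / 0.01613 = 125.3, so 126 per group (378 in total)

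Other two-sided versions give 123 (unpooled), 122 (arcsine), 127 (Kelsey) and 141 (continuity correction). None gives 103. A one-sided 5% test gives 99.

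**Step 2: power for the sized pair at 103 per group.**

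z = (0.127·√103 − 0.9992)/√0.2518 = 0.577, so power = Φ(0.577) = 71.8%

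| Method | Power at 103 per group |
|---|---|
| Pooled normal approximation | 71.8% |
| Unpooled normal approximation | 72.9% |
| Exact enumeration, uncorrected chi-square | 73.2% |
| Exact enumeration, Fisher's exact test | 65.9% |
| Exact enumeration, Yates-corrected chi-square | 65.4% |

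**Step 3: power for the hypothesis as worded.** These figures come from exact enumeration over binomial outcomes. A win means hybrid is higher with |z| > 1.96 on the uncorrected chi-square. Both wins use the same hybrid group, and that dependence is included.

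| Assumed levofloxacin rate | Hybrid vs levofloxacin, n = 103 | Both wins, n = 103 | Both wins, n = 126 |
|---|---|---|---|
| 70% | 97.6% | 72.5% | 80.6% |
| 78.3% | 73.2% | 59.6% | 69.7% |
| 80% | 62.5% | 52.5% | 62.2% |
| 82% | 48.1% | 41.9% | 50.3% |
| 85% | 26.6% | 24.4% | 29.1% |
| 88% | 10.6% | 10.2% | 11.4% |

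Hybrid versus levofloxacin alone reaches 80% at 103 per group only if levofloxacin eradicates in about 77% or fewer. For 80% power on both wins, the size would be 153 per group with levofloxacin at 78.3% and 227 per group at 82%.

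**Step 4: one three-group chi-square test instead.** With 2 degrees of freedom, 103 per group and 400,000 simulated trials, power is 74.3 / 64.6 / 62.5 / 67.2 / 77.9% for levofloxacin at 78.3 / 82 / 85 / 88 / 91%. At lower assumed rates it passes 80%: 84.6% at 75% and 95.5% at 70%. A significant overall test would not by itself show that hybrid is best.

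**Step 5: precision for hybrid minus levofloxacin.** The 95% half-width is 1.96·√[(0.91·0.09 + pL(1−pL))/103]. It is 9.7 / 9.3 / 8.8 / 8.4 / 7.8 percentage points for pL = 78.3 / 82 / 85 / 88 / 91%, against a planned difference of 12.7 points for the sized pair.

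**The case against.** The strongest reply concerns the second problem. The hypothesis is framed as an expected result, the research question is open, and the first objective is only to assess the efficacy of the three regimens. Nothing says both pairwise tests must be significant, so joint power is a criterion brought to the plan. The sample size text already shows which pair was used, and giving a third arm the same n is common practice. The joint figures also depend wholly on assumed levofloxacin rates. At 70% the loss beyond the sized pair is almost nil (72.5% against 73.2%), and a three-group test would exceed 80% if levofloxacin were at about 75% or below.

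Much of this is fair. The joint table describes a range of scenarios and does not measure one defect, and its 72–73% ceiling applies only if both pairwise wins are required. But the hypothesis does name both comparators, and a trial that does so should state what it assumes about each.

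None of this touches the first problem, which needs no levofloxacin rate. The nearest route to 80% is a one-sided 5% test, with about 81.5% power at 103. The plan says two-sided, and the one-sided formula gives 99, not 103. Inflating 99 for 3% drop-out would give 103, but the protocol states neither step.

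One further point makes matters worse for the plan: 72–73% is the favourable case. Fisher's test, also named in the analysis plan, gives about 66%, and any drop-out or multiplicity adjustment would lower power again.

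**Conclusion.** The concern holds and should be corrected.

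- **Sized pair.** With 91% versus 78.3%, two-sided 0.05 and no drop-out, 103 per group gives about 72–73% power by uncorrected chi-square, not 80%. About 126 per group would be needed. This rests only on the protocol's own figures.
- **Full hypothesis.** Power for hybrid versus levofloxacin is unstated because no rate is assumed. If the hypothesis is read as two pairwise wins, power at 103 per group runs from about 73% down to 10% as the assumed levofloxacin rate rises from 70% to 88%. Moving to 126 per group does not cure this.

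The design remains usable. Its stated power is wrong for one comparison and absent for the other.

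**What to change.** In the Sample size section:

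1. Recheck the OpenEpi inputs. If 103 per group is kept, replace 80% with the recomputed 72–73%, name the test (uncorrected chi-square, with about 66% for Fisher's exact test), and say that it refers to hybrid versus reverse hybrid only.
2. Add a short table of power for hybrid versus levofloxacin, and for both comparisons together, over assumed levofloxacin rates below 91% (for example 78–88%).

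In the Statistical analysis plan:

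3. Report hybrid versus levofloxacin as a risk difference with a 95% confidence interval, and state that a non-significant result there is not evidence of equal efficacy.

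The cost is some protocol wording and a small table, with no added patients. The downside is that the stated power becomes less favourable, for the sized pair and for the hypothesis as a whole.

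### 103 patients per group gives about 72% power, not the stated 80%, for 91% versus 78.3%; the stated inputs need about 126 per group

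*Combined protocol and SAP*

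**What the plan says.** Under Subjects and Methods, Technical Design, B) Sample size, the assumption is "Assuming that the eradication rate in patients receiving Hybrid therapy is 91% versus 78.3% in Reverse Hybrid therapy". The conclusion follows at once: "So, the sample size is 309 (103 in each group), using OPEN EPI at power 80% and C.I 95" per cent. The Operational design section repeats 103 for each of the three groups and 309 overall.

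The Statistical analysis plan names the test, "Comparison of categorical data will be performed using the Chi-square test and Fisher exact test when appropriate", and the significance rule: two-sided, "p<0.05 will be considered significant". (The alpha symbol printed beside that rule reads 2. It looks like shorthand or a slip for two-sided and does not affect the calculation.)

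The sample-size paragraph names the software but no formula. It gives no drop-out allowance, no multiplicity adjustment and no assumed eradication rate for the levofloxacin group.

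**The concern.** A two-proportion calculation needs two rates, a significance level with its sidedness, a power and an allocation ratio. All of these can be read from the document, so the stated 103 can be checked. It looked too small for a 12.7-point difference at these rates.

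This is the plan's only sample-size justification, and hybrid versus reverse hybrid is the only contrast with stated rates. If the power is overstated, a non-significant result could be read as similar efficacy from a trial believed to have an 80% chance of detecting the difference. Any loss before the retest, which comes at least one month after treatment, would lower the power further.

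**Working it through.** **Inputs.** p1 = 0.91 and p2 = 0.783, 80% power and 95% confidence come from B) Sample size. The two-sided test comes from the Statistical analysis plan. Equal allocation comes from the stated 103 in each group. So z for two-sided 5% is 1.960 and z for 80% power is 0.8416.

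**Intermediate values.**
- d = 0.91 − 0.783 = 0.127; d² = 0.016129
- mean rate p̄ = (0.91 + 0.783)/2 = 0.8465; p̄(1 − p̄) = 0.12994
- p1(1 − p1) + p2(1 − p2) = 0.08190 + 0.16991 = 0.25181
- (1.960 + 0.8416)² = 7.849

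**Attempt to reproduce 103 (n per group).**
- Fleiss, no correction: [1.960·√(2 × 0.12994) + 0.8416·√0.25181]² / d² = (0.9992 + 0.4223)² / 0.016129 = 125.3, so **126**
- Fleiss with continuity correction: (125.3/4) × [1 + √(1 + 4/(125.3 × 0.127))]² = 140.6, so **141**
- Kelsey: 2 × 0.12994 × 7.849 / 0.016129 = 126.5, so **127**
- Unpooled variance: 0.25181 × 7.849 / 0.016129 = 122.5, so **123**

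The smallest of these is 20 per group above 103. Against 126 the shortfall is 23/126 = 18%; against 141 it is 38/141 = 27%.

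**Power at 103 per group.** Normal approximation: Φ{[0.127·√103 − 0.9992] / √0.25181} = Φ{(1.2889 − 0.9992)/0.5018} = Φ(0.577) = **71.8%**. Summing over all possible outcomes of two binomials with n = 103:

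| Test | Power |
|---|---|
| Pearson chi-square, uncorrected | 73.2% |
| Fisher exact | 65.9% |
| Chi-square with Yates correction | 65.4% |

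The same normal formula at 126 per group gives 80.2%.

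**Difference detectable with 103 per group.** Holding hybrid at 91%, the uncorrected Fleiss formula returns 103 when the comparator is 76.7%: 91 − 76.7 = 14.3 points.

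**Single changes that might explain 103** (n per group, two-sided 5% and 80% power unless stated):

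| Change | Kelsey | Fleiss | Fleiss, corrected |
|---|---|---|---|
| One-sided 5% | 100 | 99 | 114 |
| 70% power | 100 | 99 | 114 |
| 2:1 split, smaller group, hybrid smaller | 106 | 98 | 110 |
| 2:1 split, smaller group, reverse hybrid smaller | 84 | 90 | 101 |

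None gives 103, and each conflicts with the stated two-sided test, 80% power or equal groups. A drop-out allowance added to the two-sided figure only moves it further from 103.

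**Effect of loss to retest (assumed rates, for illustration).** 5% loss leaves about 98 per group and 69.6% power; 10% leaves about 93 and 67.3% (normal approximation).

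**The case against.** The best defence is that 103 came from a calculation the paragraph does not describe. Three routes come close:

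- **One-sided with a small drop-out allowance.** The hypothesis is directional. One-sided 5% gives 99 by Fleiss, and power at 103 would be 81.5%. Adding 3–5% drop-out gives 102–105. But no drop-out is stated and the analysis plan says two-sided.
- **Unequal allocation.** A 2:1 split with continuity correction gives 101 + 202 = 303, close to the 309 total. The plan has three equal groups.
- **A three-group chi-square test.** With levofloxacin also at 91%, power at 103 per group is 80.0%. No such rate is stated, and it conflicts with the hypothesis that hybrid beats both other regimens. Assumed levofloxacin rates of 78.3% to 88% give about 61–70%.

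What stands is that the origin of 103 cannot be known, because no formula is given. If one of these routes was used, the paragraph is still wrong as written, because it reports different conditions.

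A second fair point concerns Fisher's test, which the plan reserves for when it is appropriate. At the assumed rates the expected failures are 103 × (1 − 0.8465) = 15.8 per group, far above the usual threshold of 5, so the ordinary chi-square would apply. The figure to carry forward is therefore 72–73%; 66% applies only if Fisher is used anyway.

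Third, the shortfall biases no estimate and does not raise the false-positive rate. That is true, but the stated power remains an error of fact.

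**Conclusion.** The concern holds. For 91% versus 78.3% at two-sided 5% with equal groups, 80% power needs 126 per group (123 to 127 by the uncorrected formulas, 141 with continuity correction). The planned 103 gives 71.8%, or 73.2% by exact enumeration of the Pearson test. The risk of missing the assumed difference is about 27–28% instead of 20%, and about 34% if Fisher's test were used.

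This rests on the plan's own rates, one unadjusted pairwise comparison, and every randomised patient being retested. Loss to retest or a multiplicity adjustment would widen the gap.

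**What to change.** Correct the sample-size statement in one of two ways.

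1. **Keep 103 per group and restate the power.** Suggested wording: *With 103 patients per group, power to detect 91% versus 78.3% is about 72% at two-sided 5% (normal approximation; 73% by exact enumeration of the uncorrected chi-square test), assuming no drop-out. Power of 80% is available for a difference of about 14.3 points (91% versus 76.7%).* This costs one sentence and no patients; the stated power becomes less favourable.
2. **Keep 80% power and change the number.** Quote 126 per group, 3 × 126 = 378 in total, which is 69 more patients than 309. State that this covers one unadjusted pairwise comparison with complete retesting. A Bonferroni adjustment would need 152 per group for two comparisons or 168 for three, before any drop-out allowance.

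In either case, name the formula, state the sidedness and allocation in the sample-size paragraph, and make the formula match the planned test. If 103 came from a calculation not described, report its actual inputs and reconcile them with the two-sided rule and the equal groups.
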